## LIST OF ABBREVIATIONS

ART	Antiretroviral Therapy
AUDIT	Alcohol Use Disorders Identification Test
BL	Baseline
BSI	Brief Symptom Inventory
CASI	Computer Assisted Self Interview
CBT	Cognitive Behavioral Therapy
CBST	Cognitive Behavioral Coping-Skills Training
CET	Comparative Effectiveness Trial
DAST	Drug Abuse Screening Test
EMR	Electronic Medical Record
E-TAU	Enhanced Treatment as Usual
FU	Month Follow-Up
ICD	International Classification of Diseases
IP	Immediate Post-Test Assessment
IRB	Institutional Review Board
MI	Motivational Interviewing
MITI	Motivational Interviewing Treatment Integrity Coding System
NIAAA	National Institute on Alcohol Abuse and Alcoholism
NIH	National Institute of Health
PI	Principal Investigator
PID	Participant Identification Number
PLUS	Positive Living through Understanding and Support
QA	Quality Assurance
RA	Research Assistant
TAU	Treatment as Usual
VAS	Visual Analogue Scale
VL	Viral Load

## PLANNED STUDY DESIGN

## STUDY OBJECTIVES

Our goals were to better understand alcohol-related outcomes among HIV-positive persons over the lifespan and to implement a multisite comparative effectiveness trial (CET) in real-world clinical settings with three intensities of treatment to test their relative effectiveness in improving ART-adherence and alcohol-related outcomes among HIV-positive individuals who drink alcohol at harmful or hazardous levels. We aimed to achieve the following four Specific Aims:

**Aim 1: Adapt the PLUS intervention for delivery in HIV clinic settings by mental health providers, and incorporate booster sessions designed to sustain longer-term effects.** We aimed to conduct formative research, and utilize our findings as well as capitalize on existing systems and approaches utilized by SCCH (e.g., text messaging) to adapt PLUS for delivery in clinic settings as well as to develop booster sessions.

**Aim 2: Test the effectiveness of the PLUS intervention delivered in a consortium of HIV clinics in New York City using a multisite CET with three intensities of treatment.** Our primary goal was to test the PLUS intervention—an efficacious, theory-based intervention that integrates MI and CBST—versus an eTAU condition and TAU alone in reducing alcohol use and improving ART adherence, viral, and immunologic outcomes among HIV+ hazardous drinkers.

**Aim 3: Assess the cost-effectiveness of PLUS.** If effective, we aimed to conduct analyses to assess the cost-effectiveness of PLUS in treating HIV+ hazardous drinkers compared to eTAU and TAU alone as estimated over 5- and 10-year windows.

**Aim 4: Collect and analyze retrospective cohort data and prospective natural history data, via Electronic Medical Records (EMR) at the SCCH clinics.** We aimed to conduct retrospective cohort analyses to compare virologic, immunologic, medical outcomes, and adherence to medical appointments/engagement in care between those who do (n = 1505) and do not (n = 3692) meet diagnostic criteria for alcohol abuse/dependence. We aimed to use the third SCCH clinic (which will not receive any intervention) as a natural history comparison group, and conduct prospective analyses of data to better understand the natural history of the intersection between problematic alcohol use and HIV medication adherence and HIV health outcomes. Of particular focus were analyses of potential differences by age, race/ethnicity, gender, sexual identity, viral hepatitis co-infection, years living with HIV, and years on ART.

## **Trial Design**

This study utilized a CET design to evaluate the effectiveness of the PLUS intervention components against a waitlist condition, and for VL and CD4, against a No-Treatment control group. Four sites were distributed across three study conditions in a quasi-experimental design. Two sites (Sites 1 and 2) implemented immediate treatment (Condition 1). Immediately after baseline, participants were offered the PLUS intervention. Participants then completed follow-up assessments at 3, 6, 9, 12, 15 and 18 months post-baseline. Site 3 implemented both the waitlist condition (Condition 2) from March 26, 2015 to October 31, 2016, and an immediate condition. Due to challenges in participant accrual, this site shifted to enrolling participants in the immediate intervention condition from November 1, 2016 through the end of the study. Participants in the waitlist condition received the intervention following completion of their 12-month follow-up. Site 4 is the no-Treatment Control EMR Group.

## **METHODS: Participants, Interventions and outcomes**

### **Inclusion Criteria**

- 18 years of age or older
- HIV-positive
- Currently receiving ART
- Current VL >200 copies/ml
- Report drinking at hazardous levels, operationalized as exceeding 14 standard drinks per week for men or exceeding 7 standard drinks per week for women, as per NIAAA guidelines. In a later amendment, criteria were expanded to also include reported use of illicit drugs exclusive of marijuana or illicit use of prescription opioids within the past 3 months.
- Must be a current patient at the clinic with current lab results

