### **Enrollment in Immediate and Waitlist control conditions**

Potential participants in the immediate and waitlist control conditions were identified through a prescreening review of EMR, which provided study staff members with lists of patients with scheduled clinic visits who had one or more detectable viral load within the past year. Study staff approached these patients during clinic visits to introduce PLUS and invited them to participate in screening. Participants provided verbal consent for screening and provided written informed consent if they were eligible and interested in enrolling. They also granted permission for the study team to abstract their EMR data for study screening and enrollment purposes.

Once consent to use the EMR was granted, eligibility criteria were verified for ART regimen and viral load. Participant self-report was used to determine alcohol and substance use criteria on the screening questionnaire. Eligible participants who enrolled in the study were scheduled for a baseline visit, which could take place the same day post-screening or be scheduled within the ensuing month. The full protocol was approved by the institutional review boards at Hunter College and Mt Sinai.

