## **Selection of No Treatment control patients**

The EMRs of randomly selected patients who belonged to the TAU site and were not enrolled in the PLUS trial were matched on key patient characteristics for comparisons with EMRs of patients in the PLUS intervention and Waitlist control conditions. This matched cohort of patients received care at a fourth clinic that did not receive any intervention (i.e., PLUS or eTAU) and was considered as a natural history comparison group. We generated a pool of patient records from which to randomly select the TAU matched cohort of patients ( $n = 120$ ). We included patient records of patients with an HIV diagnosis who had at least 1 primary care visit at the TAU clinic, received ART, and had a viral load (VL)  $>200$  copies/mL during the PLUS enrollment period from March 26, 2015 to March 16, 2017. EMRs of 20 patients who were enrolled in PLUS and possibly transferred to receive HIV care at the TAU clinic during the study period were excluded. Additionally, records of 9 patients with only one primary care visit and no follow-up visits during the study period were excluded from the pool of patient records.

Case control matching using the pool of patients meeting the criteria described above allowed us to randomly select the TAU cohort of 120 patients while matching as closely as possible to patients enrolled in the trial on key variables: age group (with ranges 18-29, 30-39, 40-49, and 50 or older), racial and ethnic identity (Black, Hispanic/Latinx, White, Asian/Pacific Island, Other/Multiracial), and gender (recorded as male or female). Additionally, we matched on indicators of substance misuse based on EMRs of trial participants using documentation of substance use problems or ICD-10 diagnostic codes, such as documentation of alcohol abuse or dependence, having had a substance use diagnosis, or any indication of substance misuse during the study period. EMRs were then extracted for the TAU cohort of patients similar to the records

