### **Data Analysis Plan**

To assess the effectiveness of our randomization procedure, we used chi-square tests and ANOVAs to investigate the equivalence of possible cofounders across each of the PLUS-enrolled four site/conditions at baseline. Specifically, we examined proportional differences across demographic characteristics (race and ethnicity, sexual and gender identity, and education), and mean differences across age and baseline outcome values (alcohol severity, drug use severity, medication adherence, viral load, and CD4). Where cell sizes were too small ( $n < 5$ ) to permit chi-square tests, we utilized a Fisher's exact test, at  $p < .05$ . The matching of the No Treatment control group ( $N = 120$ ) was assessed by bivariate comparisons with the entire PLUS-enrolled sample ( $N = 174$ ) on the available variables of age, race and ethnicity, and gender.

We also conducted analyses to test for the presence of differential attrition between conditions and sites where appropriate. First, we conducted chi-square analyses to test for differential attrition by site and study arm at each follow-up. We also tested for differential attrition at each follow-up across site, as well as several demographic characteristics (race and ethnicity, sexual and gender identity, and education). Finally, we conducted a series of point-biserial correlations to examine attrition at each wave by age and baseline outcome values (alcohol severity, drug use severity, medication adherence, viral load, and CD4).

Outcome analyses were conducted using piece-wise longitudinal growth curve models, adjusting for baseline scores on the corresponding outcome and, for the models predicting medication adherence, AUDIT, and DAST, we also adjusted for gender identity and sexual orientation, whereas for the models predicting viral load and CD4 we adjusted for gender (male, female) as sexual identity was not indicated in the EMR records for the matched cohort. For the

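### If the undated drug-use amendment took effect during enrolment, the waitlist and immediate cells may differ in drug-only share, and the adherence, viral load and CD4 models hold no term that would adjust for it

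*Combined protocol and SAP*

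**What the plan says.** **Eligibility.** The Inclusion Criteria first define the substance-use requirement as drinking above a weekly threshold. They then add: "In a later amendment, criteria were expanded to also include reported use of illicit drugs exclusive of marijuana or illicit use of prescription opioids". The natural reading is an alternative route, so that a person below the drinking threshold could enter on drug use. The amendment is undated, and no counts by route are given. Under Enrollment in Immediate and Waitlist control conditions, "Participant self-report was used to determine alcohol and substance use criteria on the screening questionnaire".

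**Allocation.** Trial Design states: "Four sites were distributed across three study conditions in a quasi-experimental design". Sites 1 and 2 delivered immediate PLUS. "Site 3 implemented both the waitlist condition (Condition 2) from March 26, 2015 to October 31, 2016, and an immediate condition"; after accrual difficulties, "this site shifted to enrolling participants in the immediate intervention condition from November 1, 2016 through the end of the study". Selection of No Treatment control patients gives the outer dates: "during the PLUS enrollment period from March 26, 2015 to March 16, 2017".

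**Analysis.** The Data Analysis Plan describes its growth-curve approach as "adjusting for baseline scores on the corresponding outcome and, for the models predicting medication adherence, AUDIT, and DAST, we also adjusted for gender identity"; sexual orientation is a further covariate in those three models. The viral load and CD4 models use gender alone beyond the baseline value. Clinic and condition enter as one four-level dummy-coded factor. The EMR cohort is added as the referent for viral load and CD4 only. Baseline alcohol and drug severity are compared across the enrolled cells, but no adjustment is tied to the result. No model, subgroup or sensitivity analysis uses entry route or enrolment before versus after the amendment.

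**The concern.** The waitlist is the only untreated comparator for AUDIT, adherence and DAST, and the untreated comparator among enrolled participants for viral load and CD4. It stopped enrolling before the trial did, and its window does not overlap that of Site 3 immediate. An eligibility change inside the enrolment period would therefore fall unevenly across the cells, and there is no randomisation to balance it.

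People admitted for recent heavy drinking and people admitted on drug use alone may follow different adherence and viral load courses, and may regress to the mean differently on AUDIT. A difference in entry mix could then be read as an effect of PLUS, or could hide one. The clinic-and-condition factor does not help, because entry mix would be confounded with that factor itself. The most exposed contrast is Site 3 immediate versus waitlist, the only comparison of treated and untreated participants within one clinic.

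The plan itself treats substance-use profile as important: the EMR cohort was matched on indicators of substance misuse.

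**Working it through.** The documents give no figure for entry mix, so there is nothing to reproduce. What can be checked is how far the eligibility eras could differ between cells, for each possible amendment date.

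**Inputs from the documents (days counted inclusively)**
- Waitlist, March 26, 2015 to October 31, 2016: 586 days.
- Site 3 immediate, November 1, 2016 to the end of PLUS enrolment on March 16, 2017: 136 days.
- Whole enrolment period: 586 + 136 = 722 days. The waitlist was open for 586/722 = 81% of it.

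**Assumptions (not in the documents)**
- Accrual is uniform within each cell.
- The amendment took effect at all sites on one date.
- Sites 1 and 2 enrolled for all 722 days.

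**Formulas.** Let k be the number of days from March 26, 2015 to the amendment, between 0 and 722. The share of each window after the amendment is:
- waitlist: max(0, 586 − k)/586
- Sites 1 and 2: (722 − k)/722
- Site 3 immediate: min(136, 722 − k)/136

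| Amendment in force | k | Waitlist | Sites 1–2 | Site 3 immediate | Gap, Sites 1–2 | Gap, Site 3 |
|---|---|---|---|---|---|---|
| by Mar 26, 2015 | 0 | 100% | 100% | 100% | 0 | 0 |
| Sep 26, 2015 | 184 | 69% | 75% | 100% | 6 | 31 |
| Mar 20, 2016 | 360 | 39% | 50% | 100% | 12 | 61 |
| Jul 1, 2016 | 463 | 21% | 36% | 100% | 15 | 79 |
| Nov 1, 2016 | 586 | 0% | 19% | 100% | 19 | 100 |
| Jan 1, 2017 | 647 | 0% | 10% | 55% | 10 | 55 |
| after Mar 16, 2017 | 722 | 0% | 0% | 0% | 0 | 0 |

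Gaps are percentage points relative to the waitlist, computed before rounding. Up to k = 586 the Site 3 gap is k/586, so it rises to 100 points at November 1, 2016. After that it is (722 − k)/136 and falls to zero. The Sites 1–2 gap peaks at the same date, at 136/722 = 19 points.

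One part does not need uniform accrual. If the amendment was in force by November 1, 2016, Site 3 immediate is wholly post-amendment. If it came later, the waitlist is wholly pre-amendment.

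**From era to entry route.** If a fraction q of post-amendment entrants are drug-only, the same in every cell, the gap in drug-only share is q times the gap above. For March 20, 2016 and q = 20% to 50% (assumed), the drug-only shares are 8–19% in the waitlist, 10–25% at Sites 1–2 and 20–50% in Site 3 immediate.

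**Illustrative bias.** If drug-only entrants differ by d SD in the adjusted outcome, bias = gap × q × d. With d = 0.3 (assumed; the result scales in proportion to d) and the largest gaps:
- Site 3 immediate versus waitlist: 1.00 × 0.2 × 0.3 = 0.06 SD to 1.00 × 0.5 × 0.3 = 0.15 SD.
- Sites 1–2 versus waitlist: 0.188 × 0.2 × 0.3 = 0.01 SD to 0.188 × 0.5 × 0.3 = 0.03 SD.

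**What the models hold**

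| Model | Own baseline | Other alcohol or drug term |
|---|---|---|
| VAS adherence | yes | none |
| Viral load, CD4 | yes | none |
| AUDIT | yes (alcohol) | no drug term |
| DAST | yes (drugs) | no alcohol term |

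**The case against.** The strongest reply is that no imbalance has been shown. A reader might infer that the cells do contain different proportions of drug-only entrants, or that their eligibility eras differ whatever the amendment date. The documents support neither. The amendment is undated, no counts by route are given, and an amendment in force before enrolment opened or after it closed gives no gap. Its description as later, and the accrual difficulties at Site 3, make a date inside enrolment plausible but do not prove it. This part stands.

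Other points also stand, in part:
- **Sites 1 and 2.** The gap is at most 19 points and the illustrative bias at most 0.03 SD. The concern is mainly about Site 3 immediate.
- **AUDIT and DAST.** Each model adjusts for its own baseline, a partial proxy for entry route. These models are less exposed than those for adherence, viral load and CD4.
- **Overlap of populations.** Drug use was never an exclusion, so early entrants who drank could also use drugs. The two groups may differ less than their labels suggest.
- **Viral load.** Every entrant needed more than 200 copies/ml, and the model adjusts for baseline viral load. Different regression to the mean by route is possible here but not shown.
- **EMR cohort.** It is the referent for viral load and CD4 and was matched on substance-misuse indicators. But it was matched to trial participants in general, not cell by cell, so the matching does not balance the enrolled cells against each other.
- **Baseline comparison.** Alcohol and drug severity are compared across the cells, so an imbalance might be seen. The plan does not say what follows if it is.

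A reader might also assume that a drug-criterion flag exists for everyone. The documents do not say whether drug items were on the screener before the amendment.

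**Conclusion.** The concern holds in conditional form. If the amendment took effect during enrolment, the waitlist and immediate cells may differ in drug-only share, by an amount that cannot be determined from the documents. Under uniform accrual, a single effective date and Sites 1 and 2 open throughout, the gap in post-amendment share is 0 to 100 points for Site 3 immediate, peaking for an amendment at about November 1, 2016, and 0 to 19 points for Sites 1 and 2. The SD figures are illustrations that depend on an assumed drug-only fraction and an assumed outcome difference.

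The gap in the analysis is clearest for adherence, viral load and CD4, and partial for AUDIT and DAST. Although the Data Analysis Plan refers to a randomisation procedure, Trial Design describes allocation by site and period, so balance on entry route cannot be taken for granted. The change is worth making because it is cheap, but the documents do not show that any result is in fact biased.

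**What to change.** In the Data Analysis Plan:
1. Add baseline AUDIT and baseline DAST together as covariates on the intercept and slope in the adherence, AUDIT and DAST models. An alternative is a yes/no indicator for meeting the drinking criterion at screening.
2. Do the same for viral load and CD4 in models limited to the 174 enrolled participants, because the EMR cohort was not screened or assessed in the trial. Keep the models that include the EMR cohort alongside.
3. Add a sensitivity analysis restricted to participants who met the hazardous-drinking criterion. If the waitlist has no drug-only entrants, covariate adjustment extrapolates; the restriction avoids this.
4. State the date on which the amendment took effect, and report entry-route counts for each enrolled cell.

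No new data collection is needed: AUDIT and DAST are baseline measures, and the drinking criterion was determined for eligibility at screening. The price is one or two more parameters per growth factor in what may be small cells, and fewer participants in the sensitivity analysis. Because the plan describes analyses already done, the added analyses should be labelled as such. They deal only with the entry-route part of the confounding by site and calendar period; the rest remains.

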### **Exclusion Criteria**

- Effectiveness trials should enroll participants that reflect the population for which the treatment is intended. Thus, we are keeping exclusion criteria to a minimum and imposing few eligibility criteria to identify our target clinical population.
- Given that the PLUS manual with guided step-by-step instructions, questions, and probes, as well as various modules and hand-outs for participants are all in English, study candidates will need to be able to communicate effectively in English.

- Any thought disorder (e.g., psychosis, schizophrenia, bipolar, having severe symptoms of psychological disorder) that would impair the individual's ability to provide informed consent or interfere with the study procedure.  
**\*\*\* NOTE:** Co-morbidities such as mental health problems, i.e., depression and anxiety disorder, and drug use are NOT considered exclusion criteria. Additionally, current or previous participation in behavioral or neurocognitive studies or interventions is NOT considered an exclusion criterion.
- Intoxication or under the influence of alcohol or other substances at the time of consent that would impair the individual's ability to provide informed consent or interfere with the study procedure.

## INTERVENTION PROCEDURES

The six-session intervention is based on the PLUS (Positive Living through Understanding and Support) Clinical Protocol Manual. PLUS is an efficacious, theory-based intervention that utilizes motivational interviewing and cognitive behavioral skills training to reduce alcohol use and improve medication adherence. The participants were informed that the sessions would focus on alcohol use, other drug use and medication adherence. Sessions were delivered by a study therapist (psychologists, social workers and psychiatrists) employed at the clinics.

### Six Sessions of PLUS

#### ***Session 1: Guidance on Participant Engagement in MI***

In Session 1, the therapist spends some time talking about the participant's perception of their behaviors (drinking, substance use and medication adherence) and what types of changes they would like to make. During these first sessions, the therapist focuses on a target behavior and offers them feedback from the assessment instruments they completed at baseline. In an MI-consistent style, the therapist proceeds with strategies such as using open questions and reflections to elicit and evoke participant's readiness for change, and may move towards the planning phase collaborating on a change plan.

#### ***Session 2: Overview of Functional Analysis Session***

The second session began with re-engagement briefly summarizing the last session's major themes on alcohol, substance use and adherence, highlighting any goals or plans that were discussed. The therapist explores recent episodes of all relevant target behaviors – drinking,

using drugs, and missing doses of HIV medication in order to gain a comprehensive understanding of the common *contexts of the participant's risk behaviors*. Although in this session the therapist begins using *CBST techniques*, the goal was to continue to communicate with the participant in an *MI* consistent fashion, using “OARS” (Open Questions, Affirmations, Reflections and Summaries) reflective listening skills. As these patterns become more clear, the therapist organizes them into a *functional analysis*, which summarizes the chain (or sequence) of events, behaviors, and consequences typically involved in the target behaviors. The therapist can then examine patterns across these chains to create a *case conceptualization*. Next step involves orienting the participant to the idea that chains can be disrupted. The creation of this functional analysis provides a starting point for discussing the rationale for CBT intervention and also for planning the specific CBST skills that a particular participant might focus on.

